1.2. Endpoints

Primary EndpointsPhase 1b:

- Recommended Phase 2 Dose (RP2D) or Maximum Tolerated Dose (MTD)
- Safety and tolerability of ibrutinib in combination with durvalumab

Phase 2:

- Overall Response Rate (ORR)

Secondary EndpointsPhase 1b:

- ORR
- Disease control rate (DCR) at Week 20 (end of Cycle 5)
- Duration of response (DOR)

Phase 2:

- DCR at Week 20 (end of Cycle 5)
- DOR
- Progression-free survival (PFS)
- Overall survival (OS)

Safety Assessments

Safety and tolerability assessments include adverse events, clinical laboratory tests, and vital signs.

1.3. Statistical Hypotheses

There is no hypothesis testing for Phase 1b. The primary objective of Phase 2 is to evaluate overall response rate (ORR) for the combination therapy at RP2D. Hypothesis testing will be conducted to address this objective as follows:

Null hypothesis (H_0): $P \leq x\%$; where P denotes overall response rate.

Alternative hypothesis (H_a): $P > y\%$; where P denotes overall response rate.

For NSCLC cohort and breast cancer cohort, a true response rate of 10% (H_0) versus 25% (H_a) will be tested. For pancreatic cancer cohort, a true response rate of 5% (H_0) versus 18% (H_a) will be tested.

1.4. Sample Size Determination

The study is not powered for comparison of dose cohorts or tumor type cohorts.

Phase 1b: Dose de-escalation will follow the 6+3 design and up to four dose cohorts will be enrolled for the DLT to determine the RP2D for the combination therapy. Therefore, Phase 1b will enroll a minimum of 6 and a maximum of 36 evaluable subjects.

Phase 2: Hypothesis for the true response rate will be tested as described below independently for each tumor type cohort based on the statistical framework of Simon's optimal 2-stage design. With a 1-sided error rate of 0.05, each tumor type cohort would have 80% power based on the true response rate in the alternative hypothesis. Approximately 130 subjects (including the subjects treated at the RP2D in Phase 1b and with the tumor type) across the three tumor type cohorts will be included in the Phase 2 analyses.

NSCLC cohort and breast cancer cohort (n=18 for interim and n=43 for final per cohort):

For each of the two tumor type cohorts, a true response rate of 10% (H_0) versus 25% (H_a) will be tested and the probability of early stopping is at least 73.4% if the true response rate is $\leq 10\%$ (H_0), and no greater than 13.5% if the true response rate is $\geq 25\%$ (H_a).

An interim analysis (for futility) will be performed based on the first 18 evaluable subjects for each cohort independently. If 2 or fewer responders are observed among the 18 evaluable subjects in a cohort, the enrollment may be stopped. Otherwise, the cohort will continue to enroll an additional 25 evaluable subjects for a total of 43 evaluable subjects for the final analysis. The null hypothesis will be rejected if 8 or more responders are observed among the 43 evaluable subjects.

Each cohort will enroll subjects according to the histology ratio described in Section 1.1.

Pancreatic cancer cohort (n=17 for interim and n=44 for final):

A true response rate of 5% (H_0) versus 18% (H_a) will be tested and the probability of early stopping is at least 79.2% if the true response rate is $\leq 5\%$ (H_0), and no greater than 16.2% if the true response rate is $\geq 18\%$ (H_a).

An interim analysis (for futility) will be performed based on the first 17 evaluable subjects. If 1 or no responder is observed among the 17 evaluable subjects, the enrollment may be stopped. Otherwise, this cohort will continue to enroll an additional 27 evaluable subjects for a total of 44 evaluable subjects for the final analysis. The null hypothesis will be rejected if 5 or more responders are observed among the 44 evaluable subjects.

1.5. Planned Analyses

1.5.1. Phase 1b Analyses

The primary objective of Phase 1b is to determine the RP2D or MTD and to evaluate safety and tolerability of ibrutinib in combination with durvalumab. The secondary objectives are to evaluate efficacy and PK and PD in subjects receiving the combination regimen.

1.5.2. Phase 2 Analyses

Interim Analysis for Futility: For each tumor type cohort, the interim analysis will be performed after the first 18 evaluable subjects (for the NSCLC and breast cancer cohorts) / 17 evaluable subjects (for the pancreatic cancer cohort) completed at least one tumor response assessment or at least 3 responders (in the NSCLC and breast cancer cohorts) / 2 responders (in the pancreatic cancer cohort) were observed, whichever occurs first. Confirmation of response is not required for those responders for the interim analysis.

Final Analysis: The final analysis for both safety and efficacy will be performed at the end of the study based on all subjects treated for this study. A Clinical Study Report (CSR) will be produced when the analysis has been performed for all three cohorts.

1.6. Testing Procedure and Level of Significance

The 2-sided significance level for the final analysis of primary endpoint (ORR) will be 0.05. Analyses of secondary endpoints will be performed using the same significance level.

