
Sample Size Determination:
	
Phase 1b: 6-36 subjects for DLT assessment (6-9 subjects in up to 4 dose cohorts, regardless of tumor type)
 
Phase 2: ~130 subjects, including 6-9 subjects treated at the RP2D in Phase 1b and with the tumor type as defined for Phase 2.
 
For NSCLC* and breast cancer**:
 
 
• Interim analysis: 18 subjects of each of the 2 tumor types = 36 total
 
• Primary analysis: 43 subjects of each of the 2 tumor types = 86 total
 
 
* For the NSCLC cohort, subjects with adenocarcinoma and squamous-cell carcinoma will be enrolled at an approximate 2:1 ratio (ie, at least 15 subjects with squamous-cell carcinoma will be enrolled).
 
**For the breast cancer cohort, subjects with triple-negative and HER2-positive breast cancer will be enrolled at an approximate 2:1 ratio (ie, at least 15 subjects with triple-negative breast cancer will be enrolled).
 
For pancreatic cancer:
 
 
• Interim analysis: 17 subjects
 
• Primary analysis: 44 subjects
 
 
The Phase 2 portion will test a true response rate of 10% (H0) versus 25% (Ha) for the NSCLC and breast cancer cohorts and 5% (H0) versus 18% (Ha) for the pancreatic cancer cohort. The null hypothesis will be rejected if 8 or more responders are observed among the 43 evaluable subjects in the NSCLC and breast cancer cohorts. The null hypothesis will be rejected if 5 or more responders are observed among the 44 evaluable subjects in the pancreatic cancer cohort. With a 1-sided type I error rate of 0.05, each cohort would have 80% power based on the true response rate in the

alternative hypothesis. The above statistical design including number of subjects and number of responders for each analysis follows the statistical framework of Simon's optimal 2-stage design ([Simon, 1989](#)). The enrollment will continue while the interim analysis is performed. The decision rule for consideration of discontinuation of each cohort at the interim analysis is described in the Study Design section above.

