#### **10.4.2. Phase 2**

Hypothesis for the true response rate will be tested as described below for each cohort independently. With a 1-sided type I error rate of 0.05, each cohort would have 80% power based on true response rate in the alternative hypothesis. Approximately 130 subjects (including 6-9 subjects treated at the RP2D in Phase 1b and with the tumor type as defined for Phase 2) across the three tumor type cohorts will be included in the Phase 2 analyses (an interim analysis and the primary analysis). The Phase 2 statistical design including number of subjects and number of responders for each analysis follows the statistical framework of Simon's optimal two-stage design ([Simon, 1989](#)). The enrollment will continue while the interim analysis is performed.

For each cohort, if a subject discontinues prior to the first tumor response assessment for reasons other than progressive disease, the subject may be replaced.

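### SAP 1.6 sets a 2-sided 0.05 level for the final ORR analysis, while SAP 1.4 and the protocol set 1-sided 0.05 with cut-offs of 8/43 and 5/44

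*SAP*

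**What the plan says.** SAP 1.6, the section on testing procedure and significance level, has two sentences. The first reads "The 2-sided significance level for the final analysis of primary endpoint (ORR) will be 0.05". The second reads "Analyses of secondary endpoints will be performed using the same significance level".

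SAP 1.4 says "With a 1-sided error rate of 0.05, each tumor type cohort would have 80% power". It then gives count rules. For NSCLC and breast: "The null hypothesis will be rejected if 8 or more responders are observed among the 43 evaluable subjects". For pancreatic: "The null hypothesis will be rejected if 5 or more responders are observed among the 44 evaluable subjects".

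The protocol agrees with SAP 1.4. Section 10.4.2 has "With a 1-sided type I error rate of 0.05, each cohort would have 80% power" and the same two cut-offs. The sample size part of the Synopsis repeats them, for example "The null hypothesis will be rejected if 8 or more responders are observed among the 43 evaluable subjects in the NSCLC and breast cancer cohorts".

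SAP 1.3 introduces the ORR hypotheses with "Hypothesis testing will be conducted to address this objective as follows" and states a pair pointing upward only: 10% against 25% for NSCLC and breast, 5% against 18% for pancreatic. It states no hypothesis for any secondary endpoint.

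SAP Table 2 plans a 2-sided 95% Clopper-Pearson interval for ORR and for DCR, and Kaplan-Meier methods for DOR, PFS and OS. It lists no test. SAP section 5, on departures from the protocol, does not mention sidedness or level.

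**The concern.** The SAP gives two significance levels for its one formal test and does not say which governs. A 2-sided 0.05 level normally leaves 0.025 in the upper tail, half of what the sample size section uses. If the published cut-offs spend more than 0.025, a cohort that lands on its success boundary could be declared positive under one section and not under the other. The study is open-label, so settling the matter after the counts are known would be a post hoc choice of primary test. If SAP 1.6 governed, the cut-offs would have to move and the stated 80% power would no longer follow from the plan's own model.

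The second sentence of SAP 1.6 adds a smaller problem. It extends a significance level to secondary endpoints for which the SAP states no hypothesis and plans no test.

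**Working it through.** **Inputs** (SAP 1.3 and 1.4; Protocol 10.4.2). NSCLC and breast: p0 = 0.10, p1 = 0.25, n1 = 18, stop at 2 or fewer, n = 43, reject at 8 or more. Pancreatic: p0 = 0.05, p1 = 0.18, n1 = 17, stop at 1 or fewer, n = 44, reject at 5 or more.

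**Formula.** With r1 the stopping count and c the final cut-off, if the stop is followed,

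P(reject | p) = sum over x from r1+1 to n1 of P(X1 = x) × P(X2 ≥ c − x), where X1 ~ Bin(n1, p) and X2 ~ Bin(n − n1, p).

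If the stop is never applied, P(reject | p) = P(X ≥ c) with X ~ Bin(n, p). Interim responders are taken to be the same subjects counted as responders at the end.

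**Step 1: reproduce the plan.** Early stopping is P(X1 ≤ r1). For 18 subjects it is 0.734 at 10% and 0.135 at 25%; for 17 subjects it is 0.792 at 5% and 0.162 at 18%. These match SAP 1.4. A search for Simon's optimal design at 1-sided 0.05 and 80% power returns exactly these two designs.

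**Step 2: size and power.**

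| Rule | Size, stop followed | Power, stop followed | Size, stop never applied | Power, stop never applied |
|---|---|---|---|---|
| 8/43 | 0.0480 | 80.0% | 0.0607 | 87.6% |
| 9/43 | 0.0209 | 73.0% | 0.0244 | 78.3% |
| 5/44 | 0.0469 | 80.4% | 0.0675 | 91.7% |
| 6/44 | 0.0170 | 74.6% | 0.0216 | 82.8% |

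The published cut-offs meet 0.05 but not 0.025 when the stop is followed. The lowest cut-offs that keep the upper tail below 0.025 are 9/43 and 6/44.

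**Step 3: the boundary count under 2-sided 0.05.** SAP 1.6 names no method, so several were tried.

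| 2-sided p-value | 8/43 | 5/44 |
|---|---|---|
| Doubled tail, two-stage, stop followed | 0.096 | 0.094 |
| Doubled tail, fixed n | 0.121 | 0.135 |
| Minimum likelihood, fixed n | 0.071 | 0.067 |
| Minimum likelihood, two-stage, stop followed | 0.060 | 0.0469 |

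For 8/43 every method exceeds 0.05. For 5/44 every method does except the last. There, no outcome in the lower direction is as improbable as 5/44, so the p-value equals the upper tail.

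**Step 4: chance of landing on that count.** Under the alternative with the stop followed: 0.8003 − 0.7304 = 0.070 for 8/43 and 0.8037 − 0.7456 = 0.058 for 5/44. If the stop is never applied: 0.094 and 0.089. Under the null with the stop followed: 0.0480 − 0.0209 = 0.027 and 0.0469 − 0.0170 = 0.030.

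**Step 5: the interval.** The 95% Clopper-Pearson interval at 8/43 is 8.4% to 33.4%, which contains 10%. At 5/44 it is 3.8% to 24.6%, which contains 5%. At 9/43 and 6/44 the lower limits are 10.04% and 5.17%, just above the null rates.

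**Step 6: another final n.** With the stop followed, a cut-off of 8 has size 0.0526 at n = 44, and a cut-off of 5 has size 0.0525 at n = 46. A cut-off of 9 has upper tail 0.0265 at n = 45.

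**The case against.** The strongest reply is that SAP 1.6 is only a loose statement of the confidence level. The count rules appear identically in the SAP and the protocol, SAP 1.6 offers no rival cut-off, and Table 2 contains only 2-sided 95% intervals. On that view the count rule dominates and nothing turns on 1.6. The likely intent may well be this, but the text does not say it: 1.6 names a significance level for the primary endpoint under a testing heading, and the interval is specified elsewhere.

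It is also true that one count per cohort is affected, with probability between 5.8% and 9.4% under the alternative, in a single-arm study that the protocol itself calls exploratory. That limits the size of the problem without removing it.

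A reader might infer more than the documents support, in three ways:

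- That both boundary counts must fail under SAP 1.6. For 5/44 this depends on the 2-sided method, which is not named.
- That the 95% interval is a competing decision rule because it contains the null rate at the boundary. No section makes it one, and a 2-sided 95% interval for estimation is compatible with a 1-sided 0.05 test.
- That power is lost whichever way the stop is used. If the stop is never applied, 6/44 keeps 82.8% power, although 9/43 has 78.3%.

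**Conclusion.** The contradiction stands in the current text and should be removed before the final analysis. The cut-offs belong to a 1-sided 0.05 design, so the defect lies in SAP 1.6. The documents do not support a claim that the sample size or the cut-offs were miscalculated.

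In NSCLC and breast, exactly 8/43 is decided differently by SAP 1.4 and SAP 1.6 under every 2-sided method examined. In the pancreatic cohort the same holds for 5/44 with equal tails, but not under minimum-likelihood ordering on the two-stage sample space.

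The 1-sided 0.05 label is itself conditional. The stop is discretionary in both documents, and if it is never applied the sizes are 0.0607 and 0.0675. The final evaluable number may also differ from 43 or 44: enrollment continues during the interim analysis (SAP 1.1) and Phase 1b subjects enter the Response-evaluable Population (SAP 2.1). With the stop followed, the level passes 0.05 at 8/44 and at 5/46. A corrected sentence should state these conditions. All figures assume that interim and final responders are the same subjects.

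**What to change.** Replace both sentences of SAP 1.6 with:

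*ORR is tested in each cohort using the rejection rules in Section 1.4 (8 or more of 43; 5 or more of 44), which correspond to a 1-sided significance level of 0.05 when the stage 1 stopping rule is followed and the final evaluable n is 43 or 44. Two-sided 95% confidence intervals for ORR and DCR are descriptive; no hypothesis test is made on secondary endpoints.*

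Label the ORR and DCR intervals in Table 2 as descriptive. Add a note giving the sizes if the stop is never applied (0.0607 and 0.0675) and at 8/44 and 5/46 with the stop followed (0.0526 and 0.0525). This changes SAP wording only: no extra patients, no new cut-offs, no protocol amendment.

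If the sponsor does intend 2-sided 0.05, SAP 1.6 should name the method. With equal tails, SAP 1.4 must change to 9/43 and 6/44, power must be restated (73.0% and 74.6% with the stop followed), and SAP section 5 must list the departure from the protocol. Those cut-offs also need recomputing at any other final n. Keeping 80% power at 0.025 per tail would take larger Simon optimal designs: stop at 2/18 then reject at 11/58, and stop at 1/18 then reject at 6/48.

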2. GENERAL ANALYSIS CONSIDERATION

Time to event or duration of event endpoints will be based on the actual event date (or censoring date) rather than visit number or visit label. Missing efficacy or safety data will not be imputed unless otherwise specified.

In general, the baseline value is defined as the last valid measurement on or prior to the first dose of study treatment. For by-visit analysis, visit windows will be used to associate assessment with a scheduled visit and will be created in reference to the date of first dose of study treatment to assign visit number based on assessment date.

2.1. Analysis Sets

Enrolled Population

This population includes all subjects who were enrolled in Phase 1b and Phase 2 (signed the informed consent and met all eligibility criteria).

Response-evaluable Population

The Response-evaluable Population is defined as all enrolled subjects who received at least one dose of study treatment (ibrutinib or durvalumab) and provided at least one post-baseline response assessment. This population includes all the qualified subjects from both Phase 1b and Phase 2. The Response-evaluable Population will be used as the primary population for analyses based on overall response rate and disease control rate at Week 20 (end of Cycle 5).

Safety Population (Treated Population)

Safety population (Treated Population) includes all subjects who received at least 1 dose of study treatment (ibrutinib or durvalumab). Subjects in this population will be analyzed as randomized for the randomized subjects. The safety population will be used to summarize the safety (including dosing) data.

DLT Evaluable Population for Phase 1b

DLT evaluable population includes Phase 1b subjects who received study treatment and did not meet the criteria for subject replacement (in Section 1.4.1) during the DLT observation period.

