### NSCLC and breast cancer:

- **Interim analysis:** n=18 per tumor type
- **Primary analysis:** n=43 per tumor type

The NSCLC and breast cancer cohorts will enroll 18 subjects per tumor type for the interim analysis and additional 25 subjects per tumor type for the primary analysis (total n=43). An interim analysis will be performed after 18 subjects are evaluable for tumor response. If a subject discontinues prior to the first tumor response assessment for reasons other than progressive disease, the subject will be replaced. If 2 or fewer responders are observed among the 18 evaluable subjects in a cohort, the Sponsor may consider discontinuation of this cohort; however, assessment of biomarkers (that may aid in prospective enrichment for responders) or tumor measurements (showing clinically relevant tumor reductions, ie, <30%, that fit the criteria for SD) may support continued enrollment.

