#### **10.1.2. Response-evaluable Population**

The Response-evaluable Population is defined as all enrolled subjects who received at least one dose of study treatment (ibrutinib or MEDI4736) and provided at least one post-baseline response (or disease) assessment. The response-evaluable Population will be used as the primary

population for analyses based on overall response rate and disease control rate at Week 20 (Cycle 5).

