*: Cohorts -1A and -1B are 2 parallel cohorts and will be enrolled concurrently in the sequence of -1A followed by -1B.

After the RP2D is determined, enrollment in Phase 2 will commence. Subjects who were not treated at the RP2D in Phase 1b will continue to be treated at the assigned dose. All subjects enrolled under Phase 1b will be followed for response evaluation and overall survival.

Phase 2:

Subjects with one of three solid tumor types (Stage III/IV) will be enrolled per the specifications below.

- NSCLC (adenocarcinoma and squamous-cell carcinoma at an approximate 2:1 ratio) (ie, at least 15 subjects with squamous-cell carcinoma will be enrolled)
- Breast cancer (triple-negative and HER2-positive cancer at an approximate 2:1 ratio) (ie, 15 subjects with triple-negative breast cancer will be enrolled)
- Pancreatic Cancer Cohort: (adenocarcinoma)

For each of the above three cohorts, the statistical framework of Simon's optimal 2-stage design will be implemented to enroll subjects (an interim analysis for futility in the first stage and the final analysis in the second stage). The interim analysis for futility will be performed to evaluate the response and safety profile. Enrollment will continue while the interim analysis is performed. A cohort may be discontinued based on the interim efficacy and/or safety results. The decisions based on the results of the interim analysis are independent in the 3 individual disease cohorts. At the time of the interim safety assessment, Investigators that enrolled subjects and the Sponsor (at a minimum: a Medical Monitor, a Drug Safety representative, and a Biostatistician) will review safety data and make recommendations for the conduct of the study: continue the trial unchanged, consider modifying in part or in whole, or stop the trial due to safety concerns.

NSCLC and breast cancer cohorts (n=43 per cohort):

The breast and NSCLC cohorts will each enroll 43 evaluable subjects. Subjects who discontinue prior to the first tumor response assessment for reasons other than progressive disease will not be considered evaluable for response. An interim analysis for futility will be performed for each cohort independently after first 18 subjects in a cohort are evaluable for tumor response. If 2 or fewer responders are observed among the 18 evaluable subjects, the Sponsor may consider discontinuation of this cohort; however, assessment of biomarkers (that may aid in prospective

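### The primary ORR set drops treated subjects who die or fail from disease and never have a post-baseline assessment, so ORR is too high relative to all treated subjects

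*SAP*

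**What the plan says.** The primary set for ORR and for DCR at Week 20 is defined in SAP 2.1 as "all enrolled subjects who received at least one dose of study treatment (ibrutinib or durvalumab) and provided at least one post-baseline response assessment". Protocol 10.1.2 is the same except that it asks for subjects who "provided at least one post-baseline response (or disease) assessment". Protocol 10.6.2.1 makes this set the ORR denominator. Neither text has a clause for a subject who dies or fails before any assessment, and SAP 2 adds: "Missing efficacy or safety data will not be imputed unless otherwise specified".

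Other sections describe evaluability differently.

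- SAP 1.1, under the NSCLC and breast cohorts only: "Subjects who discontinue prior to the first tumor response assessment for reasons other than progressive disease will not be considered evaluable for response".
- Protocol 3.1, in both the NSCLC/breast and the pancreatic paragraphs: "If a subject discontinues prior to the first tumor response assessment for reasons other than progressive disease, the subject will be replaced".
- Protocol 10.4.2, for each cohort: "if a subject discontinues prior to the first tumor response assessment for reasons other than progressive disease, the subject may be replaced".

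The decision counts use evaluable subjects. For NSCLC and breast, SAP 1.4 states: "The null hypothesis will be rejected if 8 or more responders are observed among the 43 evaluable subjects". The pancreatic rule is 5 or more of 44. The interim looks, after 18 or 17 evaluable subjects, are tied in SAP 1.5.2 and Protocol 10.6.2 to subjects who have "completed at least one tumor response assessment".

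SAP Table 2 plans ORR and DCR in the Treated population as sensitivity analyses.

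**The concern.** The first scheduled assessment is Cycle 2 Day 28 (-7 days), which is Day 49 to 56. The subjects have relapsed or refractory Stage III/IV disease, so some may die or fail before it. Protocol 7.2.4.1 and SAP Table 2 require a confirmed response, so a subject with no assessment cannot be a responder. Removing such a subject can only raise ORR, and the removal depends on outcome.

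The texts also do not agree on who counts. If only non-PD early stops are set aside or replaced (SAP 1.1, Protocol 3.1), early PD is meant to stay in, but SAP 2.1 drops it when no assessment was recorded. Symptomatic deterioration is listed apart from progressive disease in Protocol 9.2, yet Protocol 3.1 treats it as evidence of progression. Death is a reason for leaving the study in Protocol 9.3 but is not among the reasons for stopping treatment in 9.2. Two programmers could build different sets of 43 from these texts.

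At stake are the primary estimate, DCR at Week 20 and the composition of the 18/17 and 43/44 counts. The durvalumab study summarised in Protocol 1.5.4 counted as evaluable those who stopped for progression or death without a scan. This plan has no such clause.

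**Working it through.** **Inputs.** From SAP 1.4 and Protocol 10.4.2: NSCLC and breast p0 = 10%, pa = 25%, stop at 2 or fewer of 18, reject at 8 or more of 43; pancreas p0 = 5%, pa = 18%, stop at 1 or fewer of 17, reject at 5 or more of 44. Assumed, because the documents give no value: d, the share of treated subjects lost through death or disease failure with no assessment, set at 5%, 10% and 20%.

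**Step 1: reproduce the design.** With first-stage size n1, stopping limit r1, total n and rejection count r,

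P(reject | p) = sum over x from r1+1 to n1 of P(X1 = x | n1, p) × P(X2 ≥ r − x | n − n1, p).

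- NSCLC/breast: alpha 0.0480, power 0.8003, early stopping 0.7338 under H0 and 0.1353 under Ha (stated 73.4% and 13.5%).
- Pancreas: alpha 0.0469, power 0.8037, early stopping 0.7922 and 0.1621 (stated 79.2% and 16.2%).

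The plan's figures are reproduced.

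**Step 2: size of the bias.** With R responders among T treated, the evaluable denominator is T(1 − d), so evaluable ORR = (R/T)/(1 − d). The factor is 1/0.95 = 1.05, 1/0.90 = 1.11 or 1/0.80 = 1.25. Subjects lost for other reasons, such as withdrawal, would widen the gap further; they are not in d.

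**Step 3: boundary results per treated subject**, 8(1 − d)/43 and 5(1 − d)/44.

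| d | NSCLC/breast | Pancreas |
|---|---|---|
| 0 | 18.6% | 11.4% |
| 5% | 17.7% | 10.8% |
| 10% | 16.7% | 10.2% |
| 20% | 14.9% | 9.1% |

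**Step 4: type I error.** If p0 is a rate among evaluable subjects, the count among 43 or 44 evaluable subjects is still binomial with p0, and alpha stays at 4.8% and 4.7%. If instead p0 were a rate among treated subjects, the evaluable rate under H0 would be q = p0/(1 − d): 10.5%, 11.1%, 12.5% and 5.3%, 5.6%, 6.3%. Putting q into the Step 1 formula, with the interim stop obeyed:

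| d | alpha, NSCLC/breast | alpha, pancreas |
|---|---|---|
| 0 | 4.8% | 4.7% |
| 5% | 6.1% | 5.6% |
| 10% | 7.9% | 6.7% |
| 20% | 13.1% | 9.8% |

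**Step 5: interim, illustrative only.** On the same per-treated reading, the chance of meeting the stopping criterion under H0 would go from 73.4% to 70.7%, 67.7% or 60.5%, and from 79.2% to 77.6%, 75.7% or 71.2%. This assumes one response probability at both looks. The plan does not require confirmation at the interim, and lets 3 (or 2) responders trigger it early, so these figures do not model the interim as planned.

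**Step 6: power with the failures kept in.** If 25% and 18% are rates among scanned subjects, the rate in the fuller set is pa(1 − d): 23.75%, 22.5%, 20% and 17.1%, 16.2%, 14.4%. Power with the stop obeyed falls from 80.0% to 75.3%, 69.7% and 56.5% (NSCLC/breast) and from 80.4% to 77.0%, 73.2% and 64.1% (pancreas). If the targets are per treated subject, power stays at 80%.

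**The case against.** A reader might infer from Step 4 that the trial's false-positive rate is inflated, to as much as 13.1%. The documents do not support that. Protocol 10.6.2.1 defines ORR among response-evaluable subjects, Protocol 10.4.2 ties the interim count to the set in 10.1.2, and the rejection rules in SAP 1.4 are per evaluable subject. On that reading alpha does not move. The larger figures need both a per-treated p0 and an assumed 20% loss. What is unknown is only the denominators of the published rates behind p0, which Protocol 10.4.2 does not give.

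A reader might also infer that every early stop leaves the denominator. That too goes further than the text. A lesion may be assessed by scan or examination at the optional Treatment Termination visit (Protocol 8.2.3), missed evaluations are rescheduled (8.4), and subjects who stop without progression enter response follow-up (8.3, 8.3.3). Protocol 9.2 has all who stop followed for progression, and asks for documentation when progression is the reason. Eligibility is limited to ECOG 0 or 1. The affected group is therefore mainly early deaths, plus disease failures never followed by an assessment.

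The protocol also accepts a disease assessment as well as a response assessment. SAP 5, which lists major changes from the protocol, does not mention narrowing this, so the omission in SAP 2.1 looks like drafting. The Treated-population ORR and DCR will show the difference.

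All of this limits the size and stands. It does not supply the missing clause, it does not reconcile SAP 2.1 with SAP 1.1 and Protocol 3.1, and the decision counts do not use the Treated-population result.

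**Conclusion.** The concern holds as a bias in the estimate and a conflict in definitions. It is not an established inflation of type I error. The direction is certain: treated subjects who die or fail from disease and are never assessed are non-responders, and the primary set leaves them out. The size is 1/(1 − d), or 1.05 to 1.25 for an assumed d of 5% to 20%; the true d may be small given the later assessment routes. Alpha would rise only if the sponsor meant p0 per treated subject. The interim stopping figures should not be relied on. The point should be fixed, because it affects the primary estimate, DCR and the composition of the decision counts, and the remedy is wording.

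**What to change.** In SAP 2.1 and Protocol 10.1.2, define response-evaluable as:

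- treated subjects with at least one post-baseline response or disease assessment; plus
- treated subjects who died, progressed (including clinically) or had symptomatic deterioration due to the underlying disease, and never had a post-baseline assessment.

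Count only the second group as non-responders by rule. The condition must be that they never had an assessment, not that they failed before one. Otherwise a subject with suspected flare, continued under Protocol 3.1, who later has a confirmed response would be forced to non-response.

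Use this one set for the 18/17 interim and 43/44 primary counts. Align the evaluability and replacement wording in SAP 1.1, Protocol 3.1 and Protocol 10.4.2 with it, including whether replacement is mandatory or optional. Report the planned Treated-population ORR beside the 8/43 and 5/44 results; it also covers subjects who withdraw or are lost without an assessment, whom the revised set still omits.

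Cost: no new data collection. Reported ORR falls by the factor (1 − d). If the 25% and 18% targets were per scanned subject, power falls from 80% to about 75% (NSCLC, breast) and 77% (pancreas) at d = 5%, and to 70% and 73% at d = 10%. The sponsor should state which reading the null and target rates use and, if per scanned subject, whether n or the boundaries need re-deriving.
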